15.1.10. Notification of Post-Study SAEs

If an Investigator becomes aware of an SAE that may be attributable to the investigational product at any time after the end of the study, the Sponsor should be notified immediately (ie, within 24 hours) by following the instructions provided in [Section 15.1.6.2](#).

All SAEs that occur within 30 days of discontinuation from the study, whether or not they are related to investigational product, should be reported to the Sponsor within 24 hours by following the instructions provided in [Section 15.1.6.2](#).

15.1.11. Follow-Up of AEs and SAEs

All AEs must be followed during the course of the study until the AE resolves, is no longer of clinical concern, has stabilized or is otherwise explained, or the subject is lost to follow-up.

AEs ongoing at the final visit that are deemed to be “possibly, probably, or definitely” related or of other clinical significance must be followed for as long as necessary to adequately evaluate the safety of the subject or until the event stabilizes, resolves, or is no longer of clinical concern.

If resolved, a resolution date for the AE should be documented on the CRF. The Investigator must ensure that follow-up includes any supplemental investigations indicated to elucidate the nature and/or causality of the AE. This may include additional laboratory tests or investigations, or consultation with other healthcare professionals, as considered clinically appropriate by the Investigator.

All subjects showing possible drug-induced liver injury or disease progression should be followed until all abnormalities return to normal or to the baseline state. Drug-induced liver injury may develop or progress even after the causative drug has been stopped. Results should be recorded in the CRF. Note that longer follow-up can sometimes reveal an off-drug repetition of what had appeared to be drug-induced liver injury, indicating that liver injury was related to underlying liver disease.

If a subject experiences symptoms consistent with cholelithiasis or pancreatitis, the subject should have investigational product interrupted while undergoing a complete evaluation for both conditions consistent with local standards of care. If symptomatic cholelithiasis and/or cholecystitis is diagnosed, the subject should be managed and monitored as described in [Section 7.5.1](#).

If a subject is suspected to have acute pancreatitis or develops signs and symptoms consistent with acute pancreatitis, amylase and lipase levels should be monitored for 3 months after the onset of symptoms per local standard of care. If treatment-emergent acute, or nonacute pancreatitis is diagnosed, investigational product must be discontinued, and the subject should be managed and monitored as described in [Section 7.5.2](#). The Investigator should contact the Medical Monitor upon awareness of pancreatitis. Results should be recorded promptly in the eCRF.

15.1.12. Pregnancy and Follow-Up

Pregnancies are not considered AEs in and of themselves; however, if a female study participant becomes pregnant while she is enrolled in the clinical study, she must interrupt treatment with investigational product immediately (see [Table 4](#)) and the Sponsor must be notified within 24 hours of the Investigator's awareness of the pregnancy by completing the Pregnancy CRF in the EDC system and downloading and completing the Pregnancy Report Form. The Pregnancy Report Form must be emailed to [REDACTED]. The subject and neonate must be followed for outcome information and/or as considered appropriate by the Investigator and the Sponsor.

The subject may re-start investigational product when she is no longer pregnant or breastfeeding at the discretion of the Investigator and after discussion with the Medical Monitor. The subject must have a negative pregnancy test before restarting investigational product. If a subject's pregnancy is terminated early (planned or unplanned), she must have termination of the pregnancy confirmed by a serum β -hCG test before restarting investigational product.

Completing the Pregnancy Report Form is not a substitute for reporting an AE/SAE when an AE/SAE has occurred. In the situation when an AE/SAE has occurred, the AE/SAE reporting procedures described in [Section 15.1.6](#) must also be followed.

15.2. Other Safety Parameters

15.2.1. Medical History/Demographics

A complete medical history will be obtained from the subject at Screening. Smoking and alcohol consumption history and current habits will be recorded. Demographic characteristics (age, gender, race, and ethnicity) will be recorded.

15.2.2. Physical Examination

To assess for clinical findings, the Investigator or designee will perform a physical examination at the visits specified in [Table 1](#). A basic physical examination should be performed, including all body systems pertinent to the subject. Any clinically significant abnormality should be reported on the AE CRF page.

15.2.3. Vital Signs

Vital signs will be assessed at the visits specified in [Table 1](#). Vital signs include body temperature, sitting heart rate, respiratory rate, and sitting blood pressure. When taking heart rate, respiratory rate, and blood pressure readings, subjects should be seated quietly for a minimum of 3 minutes before the readings are taken.

15.2.4. Electrocardiogram

Standard 12-lead ECGs will be collected at the visits specified in [Table 1](#). All ECGs should be performed before blood draws. 12-lead ECG results will be reviewed by the Investigator or designee and findings will be recorded in the CRF as normal, abnormal but not clinically significant, or abnormal and clinically significant. Any clinically significant abnormality on ECGs should be reported on the AE CRF page.

Investigative sites must retain a copy of all 12-lead ECGs. These ECGs must be clearly labeled with the Subject ID number, date, and time. Full instructions will be provided for forwarding the 12-lead ECGs for central reading.

15.2.5. Alcohol Consumption, Smoking Habits, and Caffeine Consumption

Information about the subject's alcohol consumption, smoking habits, and caffeine consumption will be collected during the visits indicated in [Table 1](#) using the AUDIT, smoking habits, and caffeine consumption CRFs. AUDIT is a 10-item questionnaire that uses the domains of alcohol consumption, drinking behavior, and alcohol-related problems ([Saunders 1993](#))

15.2.6. Laboratory Assessments

Except for Screening and safety lab visits between regularly scheduled visits, subjects will be instructed to attend each study visit in a fasted state, preferably in the morning, and subjects should remain fasted until their blood samples have been collected. For visits that require fasting, the Investigator or designee will verify that the subject has fasted for at least 8 hours and record fasting status in the source and CRF. If the subject reports having eaten (water is permitted) within 8 hours, the Investigator or designee will document accordingly in the source

and CRF and remind the subject that fasting is required before all regularly scheduled study visits after screening (exception – safety lab visits).

Blood, urine, and stool samples for laboratory assessments will be collected at the visits specified in Table 1. Full instructions concerning the number and type of samples to be collected at each visit, the required sample volumes, sample collection methods, sample processing, labeling, and shipping will be provided in separate procedural manuals. All necessary collection supplies will be provided by the appropriate laboratory and will be appropriately assembled for the specific evaluations required at each visit.

If a subject cannot return to the clinic for a scheduled or unscheduled visit, or there is an event that triggers a need for an immediate assessment, the use of a local laboratory is required. In these cases, the Investigator will obtain the laboratory results and the laboratory normal ranges. All local laboratory data, including the reference ranges, are to be collected and entered in the eCRF within 2 days of receiving the results. For guidance on alternative processes under which subjects may complete the protocol-specified assessments under COVID-19 restrictions refer to Section 10.

All subjects with laboratory tests containing clinically significant abnormal values are to be followed regularly until the values return to normal ranges; until a valid reason, other than investigational product-related AE, is identified; or until further follow-up is deemed medically unnecessary.

The list of laboratory analytes to be tested is shown in Table 12.

Table 12: List of Laboratory Analytes to be Tested

Laboratory Assessment	Analyte
All Subjects	
Serum chemistry	Albumin, BUN, direct bilirubin (ie, conjugated bilirubin), indirect bilirubin, total bilirubin, AST, ALT, ALP, GGT, creatinine, electrolytes (calcium, chloride, magnesium, phosphorus, potassium, sodium), total protein, bicarbonate, free fatty acids (only at visits that specify analysis of this analyte), creatine phosphokinase (only at visits that specify analysis of this analyte), LDL, HDL, VLDL, total cholesterol, triglycerides, and calculation of eGFR
Hematology	Hemoglobin, hematocrit, white blood count with differential (neutrophils, lymphocytes, monocytes, eosinophils, basophils), platelets, red blood cell count (including MCV, MCH, MCHC)
[REDACTED]	
Urinalysis	pH, specific gravity, total protein, glucose, ketones, bilirubin, blood, microscopic exam, urobilinogen, albumin, creatinine, leucocytes, nitrates, albumin/creatinine ratio (if positive)
[REDACTED]	

Table 12: List of Laboratory Analytes to be Tested (Continued)

Laboratory Assessment	Analyte
Virology	HbsAg, HCV
Pregnancy Test (female subjects of childbearing potential)	β-hCG
For the Various Subsets of Subjects	
Microbiome/Metabolome Analysis	Microbiota 16S ribosomal RNA gene analysis, genome testing, fecal metabolomics, fecal bile acid analysis, and other appropriate assays to determine if and how OCA influences the composition and activity of the resident microbiota in the gastrointestinal tract

AFP = alpha-fetoprotein; ALP = alkaline phosphatase; ALT = alanine aminotransferase; AST = aspartate aminotransferase; β-hCG = beta human chorionic gonadotropin; BNP = B-type natriuretic peptide; BUN = blood urea nitrogen; DNA = deoxyribonucleic acid; eGFR = estimated glomerular filtration rate; GGT = gamma-glutamyl transferase; HbA1c = hemoglobin A1c; HbsAg = hepatitis B surface antigen; HCV = hepatitis C virus; HDL = high-density lipoprotein; IL-6 = interleukin-6; INR = international normalized ratio; LDL = low-density lipoprotein; LP(a) = lipoprotein(a); MCH = mean corpuscular hemoglobin; MCHC = mean corpuscular hemoglobin concentration; MCV = mean corpuscular volume; NAFLD = nonalcoholic fatty liver disease; NASH = nonalcoholic steatohepatitis; NFS = NAFLD fibrosis score; PAI-1 = plasminogen activator inhibitor-1; PT = prothrombin time; PTT = partial thromboplastin time; RNA = ribonucleic acid; TNF-α = tumor necrosis factor-α; TSH = thyroid stimulating hormone; VLDL = very low-density lipoprotein

The Investigator should proactively monitor and manage lipid levels in all subjects as indicated via appropriate medical interventions (eg, statins). Recent guidelines stress the importance of evaluating ASCVD risk in all subjects to help guide decisions in recommending therapies and reducing LDLc to reduce the risk and prevent onset or recurrence of ASCVD (refer to [Section 9.3.3](#) and [Appendix A](#)).

Urine-based β-hCG pregnancy tests will be performed for female subjects of childbearing potential at the visits specified in [Table 1](#). If a urine pregnancy test is positive, a serum pregnancy test must be performed to confirm the result. If positive, the Sponsor must be notified and the subject will be followed, as outlined in [Section 15.1.12](#) through pregnancy outcome.

International normalized ratio (INR) will be calculated based on prothrombin time value by the central laboratory. MELD scores will be calculated based on creatinine, bilirubin, INR, and sodium values as appropriate, collected at the same visit, with modification by United Network for Organ Sharing. If only 1 component of MELD needs to be repeated, all other components should also be repeated. Homeostatic model assessment – insulin resistance (HOMA-IR) values will be calculated based on glucose and insulin concentrations. Total OCA will be calculated based on OCA, tauro-OCA, and glyco-OCA concentrations. Laboratory analyte results may be used to calculate various cardiovascular risk and fibrosis measurement scores.

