7.4.1. Drug-Induced Liver Injury

Events of potential hepatic injury will be reviewed and adjudicated by the Hepatic Safety Adjudication Committee (HSAC) as described in [Section 16.11](#). The specific criteria for identification and adjudication of potential hepatic injury events are described in the HSAC charter.

[figure not shown]
Liver biochemistries will be evaluated to assess biochemical triggers that will prompt an immediate reevaluation of subjects. Thus, these assessments will be performed at:

- Each protocol-specified visit
- Unscheduled visits in the event of signs or symptoms of potential hepatic injury, decompensation, or if laboratory alerts have been triggered

It is important that the laboratory assessments be completed as required and that the central laboratory be used for assessments whenever possible. If a subject cannot return to the clinic for a scheduled or unscheduled visit, or there is an event that triggers a need for an immediate assessment, the use of a local laboratory is required. In these cases, the Investigator will obtain the laboratory results and the laboratory normal ranges. All local laboratory data, including the reference ranges, are to be collected and entered in the eCRF within 2 days of receiving the results. For guidance on alternative processes under which subjects may complete the protocol-specified assessments under COVID-19 restrictions refer to [Section 10](#). Local laboratory visits in conjunction with remote (telemedicine) visits are specifically encouraged in lieu of on-site visits where subject's safety is of concern (eg, adverse event monitoring).

The process for assessing subjects using specific criteria is presented in [Figure 2](#), and the specific threshold(s) for each laboratory analyte to trigger mandatory repeat testing and potentially a complete subject evaluation (depending on the repeat result) are summarized in [Table 2](#).

Figure 2: Potential DILI Management Algorithm for Study 747-303

ALP = alkaline phosphatase; ALT = alanine aminotransferase; BL = baseline; eCRF = Electronic Case Report Form; INR = international normalized ratio; IP = Investigational Product; PK = pharmacokinetic; TB = total bilirubin; ULN = upper limit of normal.

Laboratory assessments include: ALT, ALP, direct and total bilirubin, INR.

^a Signs and symptoms of hepatic injury include severe fatigue, nausea, vomiting, right upper quadrant pain, fever, rash, and eosinophilia.

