^b Lower severity treatment-emergent threshold criteria include the following from Table 2:

- 1) In subjects with normal/near normal ALT at baseline and treatment-emergent ALT $\geq 5x$ ULN, TB normal, or with Gilbert's: no change in BL TB
- 2) In subjects with elevated ALT at baseline and treatment-emergent ALT $\geq 3x$ BL or ≥ 300 U/L, whichever occurs first, TB normal, or with Gilbert's: no change from BL TB
- 3) In subjects with baseline ALP \leq ULN and treatment-emergent ALP $\geq 2x$ BL and $>$ ULN but < 250 U/L
- 4) In subjects with baseline ALP $>$ ULN and treatment-emergent ALP $\geq 2x$ BL but < 300 U/L

^c If a subject is unable to return to the site for repeat test, the subject MUST have repeat (or any safety) laboratory tests performed at a local laboratory. All local laboratory results, including reference ranges, should be entered in the eCRF within 2 days of receiving results.

^d PK sampling must be conducted within 7 days of IP interruption; close monitoring including physical exams and repeat laboratory testing should occur as often as deemed appropriate by the Investigator. In subjects with signs or symptoms of hepatic injury, the Medical Monitor should be promptly contacted upon awareness for consultation regarding management of the subject.

Table 2: Liver Laboratory Criteria for Monitoring for Potential Hepatic Injury

Baseline	Treatment Emergent	Signs and Symptoms of Hepatic Injury ^a	Action
ALT Normal/Near Normal^b	ALT $\geq 5x$ ULN TB normal Gilbert's ^c : no change in BL TB	No	
 Repeat laboratory testing including CPK within 2-4 days
	ALT $\geq 3x$ ULN Regardless of TB or DB	Yes	Interrupt 
 Repeat laboratory testing including CPK within 2-4 days Collect PK sample within 7 days
	ALT $\geq 8x$ ULN Regardless of TB or DB	No	Interrupt 
 Repeat laboratory testing including CPK within 2-4 days Collect PK sample within 7 days
	ALT $\geq 3x$ ULN TB $\geq 2x$ ULN Gilbert's ^c : DB $\geq 2x$ ULN or INR >1.5	No	Interrupt 
 Repeat laboratory testing including CPK within 2-4 days Collect PK sample within 7 days
ALT Elevated^b	ALT $\geq 3x$ BL or ≥ 300 U/L, whichever occurs first TB normal Gilbert's ^c : no change from BL TB	No	
 Repeat laboratory testing including CPK within 2-4 days

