7.6. Monitoring for Renal Impairment and Nephrolithiasis

7.6.1. Renal Impairment

[figure not shown]
AKI is a serious medical condition that may lead to chronic kidney disease or kidney failure; therefore, it is important to identify and monitor subjects for signs or symptoms suggestive of AKI for appropriate management. Investigators are instructed to evaluate for symptoms suggestive of AKI such as new onset fatigue/asthenia, nausea, or confusion and to assess signs such as decreased skin turgor (dehydration), increased heart rate, lower extremity edema, decreased urine output or dark urine at each visit.

As AKI is defined by an abrupt decrease in renal function, the Sponsor recognizes that local labs will be required to be recorded as well as all central lab data (scheduled or unscheduled visits) to adequately capture events. Repeat laboratory assessments should include albumin, serum chemistry (creatinine, BUN, electrolytes), urinalysis with microscopic examination, and assessment of estimated glomerular filtration rate (eGFR). All local laboratory data, including reference ranges, are required to be entered in the eCRF within 2 days of receiving results.

The threshold criteria used to identify and monitor subjects for potential renal impairment and the actions to be taken with investigational product are outlined in [Figure 4](#).

Baseline serum creatinine values, which will inform the subsequent decisions on monitoring for and management of renal injury, are defined as the average of serum creatinine values from the two most recent study visits (scheduled and unscheduled), that are not associated with a renal-related AE or an acute increase.

Figure 4: Algorithm for Monitoring Subjects for Potential Renal Impairment

ACE = angiotensin converting enzyme; AE = adverse event; ARBs = angiotensin receptor blockers; BUN = blood urea nitrogen; eCRF = electronic case report form; eGFR = estimated glomerular filtration rate; IP = investigational product; NSAIDS = nonsteroidal anti-inflammatory drugs.

^a Baseline value is defined as the average of the two most recent serum creatinine values from study visits (scheduled and unscheduled) that are at least 7 days apart and are not associated with an acute event or creatinine increase. Elevated results due to a renal-related AE or transient use of a nephrotoxic medication should not be included in the baseline calculations.

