### **10.5.4. Liver Laboratory Criteria for Monitoring for Suspected Hepatic Injury or Decompensation**

The evaluation of hepatic safety will include the following laboratory parameters: ALT, AST, and ALP, GGT, total bilirubin, direct bilirubin, albumin, INR of prothrombin time, and platelets.

Summary statistics will be presented by visit, including change from baseline and percent change from baseline. In addition, mean values of ALT, AST, ALP, GGT, total bilirubin, direct bilirubin, and albumin will be plotted over time.

Summaries will be repeated by baseline fibrosis stage.

In addition, the hepatic safety parameters noted above will be utilized to present analyses of worst post-baseline elevations. EAIR will be presented for each of the following parameters/criteria at any post-baseline visit:

- ALT ( $\geq$ ULN,  $\geq$ 3x ULN,  $\geq$ 5x ULN,  $\geq$ 10x ULN,  $\geq$ 20x ULN, or an increase of 250 U/L from baseline)
- AST ( $\geq$ ULN,  $\geq$ 3x ULN,  $\geq$ 5x ULN,  $\geq$ 10x ULN,  $\geq$ 20x ULN, or an increase of 250 U/L from baseline)
- ALP ( $\geq$ 2x ULN,  $\geq$ 3x ULN, or an increase of 150 U/L from baseline)

- Total Bilirubin ( $\geq 2x$  ULN,  $\geq 5x$  ULN,  $\geq 8x$  ULN, or an increase of 2 mg/dL from baseline)
- Direct Bilirubin ( $\geq 2x$  ULN,  $\geq 5x$  ULN, or an increase of 1 mg/dL from baseline)
- GGT ( $\geq 2x$  ULN)
- INR ( $\geq 1.5x$  ULN,  $\geq 3x$  ULN,  $\geq 5x$  ULN)

Evaluation of drug-induced serious hepatotoxicity (eDISH) will be conducted to visually compare maximum ALT and total bilirubin values at any post-baseline visit. For subjects with baseline ALT or total bilirubin levels above ULN, eDISH plots will also be generated based on multiples of elevations above the baseline (BL) value ( $2 \times BL$  and  $3 \times BL$  for ALT, and  $2 \times BL$  for total bilirubin).

Similar eDISH analysis as described above will be performed for ALP and total bilirubin. Plots based on multiples of elevations above the baseline value will use  $2 \times BL$  for ALP and  $2 \times BL$  for total bilirubin.

The summary table as well as visual plots will be based on central lab data. eDISH using maximum post-baseline ALT and total bilirubin will be repeated with central and local lab data.

In addition, EAIR will be presented for each of the following biochemical triggers for potential DILI by treatment group using the worst post-baseline elevations. For subjects with normal baseline liver biochemistry:

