Added Analysis of Covid-19 impact on the study	Following FDA guidance: Conduct of Clinical Trials of Medical Products During the COVID-19 Public Health Emergency	Impact of Covid-19 on protocol deviations under section 5.6  Incidence of Covid-19 infection under section 10.3  Incidences of AEs before and after Covid-19 under section 10.
Updated lab analysis	Per FDA feedbacks, additional lab data analyses related to cardiovascular, renal and hepatic injuries from both local and central laboratories have been produced in Month 18 IA resubmission and will be also done at the end of study	Updated Serum Chemistry Lipids analysis under section 10.4.9.4  Updated Liver Injury related lab data analyses under section 10.5.4.  Updated Renal injury related lab data analyses under section 10.5.6

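### SAP 10.5.4 gives the ALP/bilirubin eDISH no local-laboratory version and leaves the source of the worst-value and DILI-trigger rates open, although the protocol requires local tests for urgent liver events

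*Protocol*

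**What the plan says.** **Where urgent liver tests are done.** Protocol 7.4.1 asks that "the central laboratory be used for assessments whenever possible". It then makes a local laboratory compulsory if the subject cannot return to the clinic or an event needs immediate assessment. The general laboratory section (15.2.6) has the same rule: if "there is an event that triggers a need for an immediate assessment, the use of a local laboratory is required". A footnote to the DILI management algorithm (Figure 2) adds that, when a subject cannot get back to the site for a repeat test, "the subject MUST have repeat (or any safety) laboratory tests performed at a local laboratory".

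**What happens to the results.** Protocol 7.4.1: "All local laboratory data, including the reference ranges, are to be collected and entered in the eCRF within 2 days of receiving the results". SAP 10.5 carries local results into the laboratory analysis dataset with a flag (LOCALFL), and SAP Section 4 includes them in by-subject listings.

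**What the SAP analyses.** Section 10.5.4 states: "The summary table as well as visual plots will be based on central lab data". The next sentence adds: "eDISH using maximum post-baseline ALT and total bilirubin will be repeated with central and local lab data". No other output in that section names local data.

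**What the SAP says elsewhere.** The change table in Section 11 reports that, after FDA feedback, additional laboratory analyses "related to cardiovascular, renal and hepatic injuries from both local and central laboratories" were produced for the Month 18 resubmission and will also be done at end of study. For the liver it points to 10.5.4, and for the kidney to 10.5.6.

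**The concern.** A value recorded only at a local laboratory cannot enter a table or plot built from central results. The values most likely to be local are those from urgent or off-site work-up, which is when ALT, ALP or bilirubin may be at their peak. A worst post-baseline output that leaves them out can show a lower maximum than the subject actually had, or no threshold crossing at all.

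The stakes are in the comparison between arms. Hepatic injury is an end-of-study safety objective (Protocol 6.7, SAP 2.1.2.4), and Protocol 5.5 reports serious hepatic events as more frequent on 25 mg than on 10 mg or placebo. If urgent work-up is more common in one arm, more peaks would be lost in that arm and the difference in laboratory rates would shrink. ALP also matters for this drug: the footnotes to Protocol Table 2 describe modest early ALP rises as an expected pharmacodynamic effect. Yet the ALP eDISH is the plot with no local-data version.

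**Working it through.** The plan gives no figure to reproduce, so the check sets the texts side by side.

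**1. Can a peak exist only as a local result?** Yes. Protocol 7.4.1, Figure 2 and 15.2.6 require local testing in defined urgent or off-site situations. Nothing requires a central sample to be drawn in parallel.

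**2. Are local results available for analysis?** Yes. They are in the eCRF with reference ranges and flagged in the laboratory dataset (SAP 10.5).

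**3. Which 10.5.4 outputs use them?** The central-data sentence follows the two eDISH paragraphs, so it can be read narrowly (the eDISH table and plots) or widely (the section's worst-value outputs).

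| Output in SAP 10.5.4 | Narrow reading | Wide reading |
|---|---|---|
| ALT/total bilirubin eDISH | central, repeated with central plus local | same |
| ALP/total bilirubin eDISH | central only | central only |
| Rates of worst ALT, AST, ALP, total and direct bilirubin, GGT and INR elevations | source unstated | central only |
| Rates of combined and absolute-increase DILI triggers | source unstated | central only |

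On either reading, exactly one output is specified with local data, and the ALP eDISH is specified without it. The trigger rates are introduced after the central-data sentence, which favours the narrow reading for them, but no source is named.

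**4. Does Section 11 settle it?** No. It announces hepatic-injury laboratory analyses from both sources, in the plural, and refers to 10.5.4 for the content. There the ALT/bilirubin repeat is the only one.

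**5. Can local and central values be put on one scale?** Mostly. Section 10.5.4 fixes upper limits of normal for ALT (30 U/L), AST (35 U/L), total bilirubin (1.25 mg/dL), direct bilirubin (0.3 mg/dL) and ALP (120 IU/L). It fixes none for GGT or INR, although both have thresholds stated as multiples of the ULN. Those two need their own rule.

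**6. Kidney.** Protocol 7.6.1 recognises that, to capture acute kidney injury, "local labs will be required to be recorded as well as all central lab data". SAP 10.5.6 names no laboratory source for the worst creatinine and eGFR changes: it neither excludes nor includes local results.

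**The case against.** The strongest reply is that hepatic safety does not rest on these outputs. Under SAP 10.4.2 the hepatic safety adjudication committee reviews everything available on each identified subject, found through biochemical, adverse-event and questionnaire triggers. Rates and time to onset of adjudicated DILI are planned, and hepatic adverse-event tables are separate. All of this stands. A reader might infer that the SAP hides hepatic harm; it does not. What remains is narrower: adjudicated cases do not replace by-arm rates of threshold crossing, which the SAP plans as outputs in their own right.

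Second, the protocol prefers the central laboratory, asks subjects to return to the site where possible, and provides for liver tests at unscheduled visits. Many abnormalities will first be seen on a scheduled central panel. This also stands, and it limits the gap to urgent or off-site assessments.

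Third, a reader might infer that Sections 10.5.4 and 11 contradict each other. On the narrow reading they do not: Section 11 states an intention and 10.5.4 does not forbid local data in the rates. SAP Section 1 also refers post-CRL analyses to Addendum V2.0, which is not among the documents reviewed. But Section 1 says the present document is updated for end of study, so the end-of-study data source should be clear in 10.5.4 itself. The sections need aligning; they are not shown to conflict.

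**Conclusion.** The point holds in a limited form. Following 10.5.4 as written leaves peaks measured only locally out of the ALP/total bilirubin eDISH. It leaves open, or on the wide reading excludes, their use in the worst-elevation and DILI-trigger rates. They still reach the ALT/bilirubin eDISH repeat, the flagged dataset, the listings and adjudication.

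The size of the loss cannot be estimated from the documents. A reader might try visit spacing: after Month 18 visits are 6 protocol months apart, 6 × 4 = 24 weeks. An excursion assumed to last 2, 4 or 8 weeks would then contain a scheduled draw with probability 2/24 = 8%, 4/24 = 17% or 8/24 = 33%, which suggests that 67% to 92% are missed. At 12-week spacing the same durations give 33% to 83%. These are not miss rates for this trial. They assume that all work-up is local, that no unscheduled central sample is drawn and that onset is random relative to visits. Excursions found on the scheduled panel have a central value by construction, and the documents give neither excursion lengths nor the share of local testing.

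Nor do the documents support saying that worst renal values are central-only; their source is simply not named. The conclusion assumes only that some urgent liver assessments lack a central sample at the peak, which the protocol's rules allow.

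**What to change.** In SAP 10.5.4, extend the existing repeat sentence along these lines: *The eDISH analyses for ALT with total bilirubin and for ALP with total bilirubin, the exposure-adjusted rates of worst post-baseline threshold elevations, and the exposure-adjusted rates of DILI triggers will each be presented from central results and again from central and local results combined, with LOCALFL records included. ALT, AST, total and direct bilirubin and ALP are judged against the limits listed in this section; GGT and INR are judged against the reporting laboratory's reference range.*

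Align Section 11 with this list, and name the laboratory source for the worst creatinine and eGFR changes in 10.5.6.

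The cost is SAP text and programming. No new data are needed, since local results and their reference ranges are already required in the eCRF and flagged for analysis. There is a small downside: assays differ between laboratories, and sicker subjects are tested more often, which gives them more chances of an extreme value. Keeping the central-only version beside the combined one lets the reader see both effects.
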